9.4 SAMPLE SIZE AND ACCRUAL

9.4.1 Primary Outcome Sample Size Calculations:

Our proposed HEAL sites report an overall mortality rate of 14%. Using three large sites that participated in the phase II study (UCSF, Wash U, CNMC) we can also estimate the rates of neurodevelopmental impairment: death = 14%; moderate-severe impairment = 18%; mild impairment = 17%; and normal = 51%. Therefore, we anticipate a **control primary outcome rate of 49%** (death or NDI).

Non-human data informing treatment effect size: A recent study with nonhuman primates (*Macaca nemestrina*) compared animals experiencing 15-18 minutes of umbilical cord occlusion that were then treated with either saline (n=14), therapeutic hypothermia (n=9), or therapeutic hypothermia and multiple doses of Epo.²¹ Among animals treated with saline 8/14 = 57% died or had NDI. Among animals treated with hypothermia (HT) alone 7/9 = 78% died or had NDI, while among animals treated with hypothermia and Epo (HT+Epo) only 5/12 = 42% were observed to die or have NDI. Results from Figure 2 of Traudt et al.¹⁴⁹ (2013) show the number of animals in each outcome category by treatment group. These data suggest a risk ratio of 0.53 (95% CI: 0.25, 1.14) comparing HT+Epo to HT alone, and a risk ratio of 0.73 (95% CI: 0.32, 1.64) comparing HT+Epo versus saline. Therefore, animal data support an Epo effect that optimistically corresponds to a

50% reduction, and that is conservatively associated with a 27% reduction in the primary outcome rate.

Phase I data informing treatment outcome rates: Given that the primary outcome is based on a 22-26 month assessment we can rely on a recently completed long-term follow-up from a phase I study⁸⁴ in which 24 cooled infants were given multiple doses of Epo ranging from 250U/kg to 2500U/kg²⁴. At 22-26 months of age n=22 subjects were followed, and 0/22 subjects died, 1/22 had moderate-severe NDI, and 6/22 had mild NDI. This study suggests an **overall primary outcome rate of 7/22 = 31.8%** (exact confidence interval = 14%-55%) for our planned intervention group. We recognize that the dosing of Epo was not optimized in the phase I trial, and our proposed study will use multiple doses of 1000U/kg for all subjects which has been shown to yield plasma concentrations observed to be neuroprotective in animal studies.

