9.6 DATA AND SAFETY MONITORING PLAN (DSMP)

The DSMB will review the accruing data to: 1) ensure that the study is adequately enrolling; 2) to ensure that there are no serious safety concerns; and 3) to assess whether the study efficacy appears overwhelming. The DSMB will be assigned by NINDS. The research coordinator at each site will monitor each subject weekly for the presence of any complications. Serious adverse events will be brought to the attention of the DSMB, and if appropriate, the IRB, in writing. An independent medical monitor will review all cases of serious adverse events.

As part of this DSMP, we will perform continuous and interim analysis of accruing safety data. We have defined potentially treatment (Epo) related serious adverse events (SAEs) that will be monitored throughout the course of the study. Specifically, for SAEs we will compare absolute rates to expected rates based on published data for similar newborns, and will seek careful DSMB review and guidance when observed rates exceed pre-specified thresholds. In addition, at planned interim analysis we will formally compare the event rates across the two treatment groups using appropriate small sample methods such as Fisher's exact test. The DCC PI will remain masked to assignment while the study staff statistician will not.

The primary outcome of the study is a composite endpoint of mortality or NDI at 24 months of age. Therefore, monitoring the primary outcome for treatment efficacy or futility is challenging. Based on enrollment plans, the majority of patients will have been randomized by the time NDI is assessed at 24 months for any participants, and therefore we do not expect to be able to conduct a first interim analysis prior to the completion of enrollment. We expect to have the primary outcome evaluated on the first quarter of subjects (n=125) after 34 months of recruitment at which point we expect to have randomized n=450 of the total n=500 subjects (90% enrollment completed). Therefore, any actions that a DSMB might take to prevent subsequent patients from receiving an ineffective treatment (futility) or to make available a useful treatment (efficacy) will not have a direct impact on patients participating in

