this study. As a surrogate for long-term 24-month clinical efficacy on NDI, one alternative would be to monitor directly early MRI results as intermediate outcomes or surrogates. However, a large study published by Cheong et al.,¹⁵⁰ found that early MRI measurements had poor sensitivity (27-60%) for accurately predicting death or NDI at 2 years. Therefore, we do not recommend using early MRI measures as a surrogate for the long-term outcome for monitoring treatment efficacy. Given that we are not conducting interim analysis directly on the primary outcome measure for efficacy or futility, we do not make adjustments to sample size or statistical power to account for interim alpha spending.

Our primary objective for interim analyses is therefore to allow for careful and continued monitoring of mortality and safety outcomes. We propose to conduct formal statistical analysis and inference for mortality at three interim and one final analysis time. We will continue to present mortality and SAE data from all available follow-up data, but we expect most treatment-related safety events to occur within the first three months of follow-up. We will conduct formal safety evaluation at 6, 12, 18, and 24 months following the start of enrollment, where approximately 25, 50, 75, and 100% of the study cohort will have been randomized and followed for at least 3 months. As part of each interim analysis, we plan to monitor mortality as a primary safety endpoint and will control the overall significance level using O'Brien-Fleming boundaries (net alpha=0.05 significance, accounting for three interim and one final analysis). The DSMB will also monitor all other SAEs utilizing the same O'Brien-Fleming sequential monitoring boundaries without further adjustment for multiple comparisons, but allowing for flexibility to continue the study if the O'Brien-Fleming boundary is reached on a secondary SAE endpoint.

Table 11. O'Brien-Fleming Monitoring Boundaries

Enrollment	Monitoring p-value: Death
25%	0.000014734
50%	0.0030359
75%	0.016248
100%	0.030701

EXAMPLE SAFETY MONITORING TABLE

Shell Table 1. Closed Report: Serious adverse event (SAE) incidence rate (number of events/number at risk) and threshold for action.

Serious Adverse Events	Group A	Group B	Expected (Range)	Threshold for Action	p-value*
Systemic hypertension			0.2-3.0 ¹⁵¹⁻¹⁵³	6%	
Polycythemia			1.0-5.0% ¹⁵⁴	10%	
Disseminated intravascular coagulation (DIC)			11.0-45.0% ³⁻⁷	50%	

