### 1.2 Design

This study is a randomized parallel group double-masked, placebo-controlled trial in neonates with HIE. We will enroll 500/2 = 250 subjects in each of two treatment groups: Epo-treated vs. placebo control. Eligible neonates will be enrolled and treated with either Epo or normal saline (on study day 1,2,3,4, and 7) and followed for a fixed period of 24 months ( $\pm 56$  days) for survival and neurological outcomes. For extenuating circumstances, for example, COVID-19 restrictions, the in-person elements of the final endpoint evaluation may be performed up to 36 months of age. The follow-up period was chosen to provide meaningful motor and cognitive outcomes, since CP and motor and cognitive deficits are more reliably diagnosed at 2 years of age. Enrolled children will be randomized, stratified by study site and severity of HIE, with equal likelihood to receive Epo or saline.

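### The mortality monitoring table prints the alpha spent at each look as if it were a p-value cut-off, so the rule runs at 0.037 overall instead of the stated 0.05

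*Protocol*

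**What the plan says.** Protocol 9.6 plans "formal statistical analysis and inference for mortality at three interim and one final analysis time", at points where "approximately 25, 50, 75, and 100% of the study cohort will have been randomized and followed for at least 3 months". The plan "will control the overall significance level using O'Brien-Fleming boundaries" ("net alpha=0.05 significance, accounting for three interim and one final analysis"). SAP section 9 carries the same provision.

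Protocol Table 11 and SAP Table 6 list one value per look under the column heading "Monitoring p-value: Death": 0.000014734, 0.0030359, 0.016248 and 0.030701. The same boundaries are to be applied to every other SAE. For the test itself, the protocol says that at the planned interim analysis "we will formally compare the event rates across the two treatment groups using appropriate small sample methods such as Fisher's exact test". Neither document describes the tabulated values as alpha spent, names a spending function, or states whether the mortality test is one-sided or two-sided.

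**The concern.** The four entries add up to 0.05. Cut-offs for repeated tests on accumulating data should not do that. The test statistics at successive looks are correlated, so part of the chance of falling below a cut-off at a later look belongs to trials that already crossed earlier. For a two-sided overall level of 0.05, the nominal cut-offs from look 2 onward must therefore exceed the alpha newly spent at each look, and their sum must exceed 0.05. Entries that add up to exactly 0.05 suggest that the per-look spend was printed in place of the cut-off.

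Mortality is the primary safety endpoint of the monitoring plan. If the spend is used as the cut-off, the rule asks for stronger evidence of excess deaths than the plan says it does, and the stated overall level is wrong for mortality and for every other SAE monitored with the table.

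**Working it through.** **Inputs.** Overall alpha 0.05, four looks and information fractions t = 0.25, 0.50, 0.75, 1.00 (Protocol 9.6). Boundary values from Protocol Table 11 / SAP Table 6. For the consequences only: control mortality 14% (Protocol 9.4.1) and 250 per arm (SAP 1.2). Two-sided testing is assumed; Epo-arm mortality of 20 to 25% is an assumption, since the documents give no harm alternative.

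**Step 1: where the printed values come from.** The O'Brien-Fleming-type (Lan-DeMets) spending function for two-sided 0.05, taken as twice one-sided 0.025, is

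α(t) = 4 × [1 − Φ(z₀.₉₈₇₅ / √t)], with z₀.₉₈₇₅ = 2.2414.

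| t | 2.2414/√t | cumulative α(t) | increment | printed value |
|---|---|---|---|---|
| 0.25 | 4.4828 | 0.0000147336 | 0.0000147336 | 0.000014734 |
| 0.50 | 3.1698 | 0.00305065 | 0.00303591 | 0.0030359 |
| 0.75 | 2.5881 | 0.0192986 | 0.0162480 | 0.016248 |
| 1.00 | 2.2414 | 0.0500000 | 0.0307014 | 0.030701 |

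All four increments agree with the table to the digits printed. The printed values sum to 0.0499996.

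**Step 2: overall error if they are used as cut-offs.** As two-sided p-values they correspond to |Z| ≥ 4.333, 2.964, 2.403 and 2.161. Recursive numerical integration over the joint normal distribution of the four statistics (independent increments) gives cumulative crossing probabilities under no difference of 0.0000147, 0.00304, 0.0173 and **0.0374**. In the harm direction alone the total is 0.0187, against 0.025.

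**Step 3: can another reading rescue 0.05?** No. Read as one-sided p-values, the table gives 0.0364 in one direction and 0.0728 counting both. The classical O'Brien-Fleming cut-offs are 0.0000515, 0.00420, 0.0194 and 0.0429, which do not match the table either.

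**Step 4: cut-offs that spend 0.05.** Solving look by look for the boundary whose first-crossing probability equals each increment in Step 1:

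| look | z | nominal two-sided p | printed |
|---|---|---|---|
| 25% | 4.333 | 0.0000147 | 0.0000147 |
| 50% | 2.963 | 0.00305 | 0.00304 |
| 75% | 2.359 | 0.0183 | 0.0162 |
| 100% | 2.014 | 0.0440 | 0.0307 |

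These give a cumulative crossing probability of 0.0500.

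**Step 5: size of the consequence.** The drift is (p_Epo − 0.14) / √(0.14×0.86/250 + p_Epo(1−p_Epo)/250). At 22% this is 0.08/√(0.0004816 + 0.0006864) = 2.34. Chance of having signalled excess Epo deaths, by simulation with a normal approximation (printed / corrected):

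| Epo mortality | by look 2 | by look 3 | by look 4 |
|---|---|---|---|
| 20% | 4.5% / 4.5% | 20.1% / 21.3% | 37.4% / 42.5% |
| 22% | 9.6% / 9.6% | 35.8% / 37.4% | 58.8% / 64.0% |
| 24% | 17.6% / 17.6% | 53.9% / 55.6% | 77.4% / 81.3% |
| 25% | 22.8% / 22.8% | 62.7% / 64.3% | 84.4% / 87.5% |

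A concrete case at the final look: 54/250 deaths against 35/250 gives a Fisher p of 0.035. That crosses 0.0440 but not 0.0307.

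**The case against.** The arithmetic is not in dispute; the case on the other side concerns how much it matters.

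- **The looks that can spare infants exposure hardly change.** The loss is nil at looks 1 and 2 and under 2 percentage points at look 3. The bulk falls at the 100% look, when everyone has been randomized and followed for at least 3 months and dosing is over. This stands: the effect on early stopping is small.
- **The error is conservative.** An overall level of 0.037 does not exceed 0.05, and the primary efficacy analysis has no interim looks, so it is untouched. True, but for a harm rule a stricter cut-off means a lower chance of signalling excess deaths.
- **Deaths are also tested at 0.05 elsewhere.** Protocol 9.3.4 and SAP 5.5 compare each SAE between arms at 0.05 with no multiplicity correction, so an end-of-study imbalance would not obviously go unreported. This is fair, but a separate test does not give the sequential rule the error rate claimed for it.
- **In deaths, the difference is small.** With 35 control deaths in 250, Fisher's test crosses at 55 Epo deaths with the printed value and 54 with the corrected one. With 26 in 188 at look 3 it is 46 against 45; with 18 in 125 at look 2 it is 39 under both. This is correct and useful for scale.
- **The corrected values are also tied to 25/50/75/100%.** Protocol Table 12 and SAP Table 7 show 60, 143, 226 and 309 of 500 evaluated for safety at months 6, 12, 18 and 24, which is 12, 29, 45 and 62%. This stands as a reason to recompute the cut-offs from the spending function at each look. It does not support keeping the printed values.

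**Conclusion.** The concern holds. The column contains incremental alpha presented as p-value cut-offs, in both documents, and the rule as written has an overall two-sided level of 0.0374 instead of 0.05. The practical loss is confined to the later looks: about 1 to 2 percentage points in the chance of a harm signal by look 3, and about 3 to 5 points by the final look, for Epo mortality of 20 to 25% against 14%.

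This rests on the stated information fractions, two-sided testing and a normal approximation; Fisher's exact test would be more conservative still. That the spending-type boundary was intended is an inference from the digit-for-digit match, because the documents do not say so. The stated 0.05 fails under every reading of the table that was tried.

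**What to change.** In Protocol Table 11 and SAP Table 6, replace the column with the nominal two-sided p-values 0.0000147, 0.00305, 0.0183 and 0.0440. Alternatively, relabel the present column as alpha spent at each look and add these cut-offs beside it. State that the boundary is the Lan-DeMets O'Brien-Fleming-type spending function at two-sided 0.05, and that the cut-offs will be recomputed at the actual information fraction of each look. Carry the change into the DSMB report template, and apply it to the other SAEs that use the same boundaries.

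The cost is one table in each of the two documents plus the template. It needs no additional patients and no new data.

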10 DATA COLLECTION, SITE MONITORING, AE REPORTING

10.1 RECORDS TO BE KEPT

All data will be entered into CRFs in the HEAL Portal that are developed specifically for the study, using a REDCap platform. These forms will include screening, enrollment and follow-up data for infants. The infant's parent or legal guardian must read, understand, and sign an IRB approved informed consent form. Additionally, it will be recorded in the infant's medical record that the infant is involved in this study. The Investigator will retain the original signed consent form in a secured location. Investigators must provide all information required by the protocol on the CRFs in the HEAL Portal provided for the study.

At the DCC, all data received is identified by a unique subject ID. No subject identifiers are collected other than date of birth

10.1.1 Subject identifiers

Only the clinical site will have the Screening Log that maps the ID number, infant initials and randomization number to the subject's name and contact information at their site. At the clinical sites, all subject data are maintained in locked file cabinet or other secure locations with limited access by researchers and staff. Laboratory samples will be identified by a study ID number. A list of each sites' subjects will be kept separately in password protected or locked files within that site investigator's office.

10.1.2 Documentation

Each site must provide the CCC at the University of California, San Francisco with the following documents prior to study initiation. A copy of these documents must also be maintained throughout the study in the investigator's study files.

- IRB approved informed consent form

- Completed 1572 form, signed and dated CVs, proof of current CITI training or equivalent (Human Subjects Training), Good Clinical Practice certification, financial conflict of interest forms, and proof of current medical licensure for all investigators
- All IRB approvals and correspondence (approved revisions, protocol, advertisements, etc.)
- Copies of all correspondence pertaining to the study (excluding any budgetary matters)
- Copies of all serious adverse events submitted to the IRB
- Copy of all safety reports

The clinical site is responsible for maintaining all records (i.e., case report forms, original data, screening logs, signed informed consent forms, correspondence, etc.) until notified, in writing, by CCC, that these records are no longer needed. The Investigator must notify CCC project director if the site or records are relocated, if the investigator leaves the institution, etc. and a new address for the records must be provided.

10.2 ROLE OF DATA MANAGEMENT

The DCC will be at University of Washington, Seattle WA. The DCC will create an https secured web-based portal specially designed for the purposes of this study. The study portal will provide a highly-structured repository to store and process study data from e-CRFs, as well as to protect its integrity and confidentiality. This tool will assist the CCC by providing efficient protocol management and study enrollment and retention oversight. Access to the study portal will be granted by the DCC with differential access rights based on role. Users at a given site will only have access to data on study participants at their own site.

The DCC is responsible for:

- Providing tools for data collection, management and monitoring for the clinical sites
- Supporting a web page and portal and providing training for research staff
- Providing and managing secure log-in access to the study portal
- Biostatistics and analysis support

The DCC also has the responsibility to:

- Generate and distribute masked randomization assignments to clinical site pharmacies
- Ensure study drug accountability at all sites
- Provide data summaries and statistical analyses for the study
- Receive information about SAEs
- Generate semi-annual data and safety monitoring reports for independent assessment by the study DSMB

The DCC will facilitate user access by sponsoring UW NetIDs for each individual involved with the HEAL project. For each clinical recruitment site, the DCC will provide up to two initial training sessions to

familiarize research staff and investigators with the web-based data management portal. As research staff turnover during the course of the study, data management training videos and a FAQ page will be accessible on the portal home page in order to ensure that new staff are facile with the system.

10.2.1 The Clinical Site responsibilities in data collection and management

10.2.1.1 Data Collection Protocol

- For screening and enrollment, the site will access the REDCap study portal via the web, provide screening information about the patient (Screening ID will be generated) and if eligible for randomization, receive the study participant number (Study ID).
- Study-related data, as outlined in the schedule of visits and evaluations above, will be entered online by site personnel directly into the CRFs within the REDCap study portal.

10.2.1.2 Description & Flow of Case Report Forms (CRFs)

- Copies (PDF versions) of all CRFs are printable from the study portal.
- CRFs can be printed and used to capture data, and later entered into the REDCap study portal.

10.2.2 Data Security and Confidentiality

The DCC employs procedural and technical controls to ensure the security, integrity and confidentiality of subject data that are in compliance with established regulations and standards for Information Technology Security. While only limited identifiable data will be collected by the DCC (date of birth, dates of service), this server room meets the technical requirements for HIPAA compliance and hosts other servers containing PHI. Multiple levels of data security are in place designed to prevent unauthorized access and limit authorized access to the computer systems and prevent data corruption and loss. These include firewall and network intrusion detection devices, malware protections, account and system security features, as well as written policies and procedures.

10.3 QUALITY ASSURANCE

We will monitor the accuracy of data entry by the sites both internally and externally. For internal monitoring, completed online CRFs (in the HEAL Portal) are reviewed on a regular basis, and issues are clarified as necessary with site coordinators who act as liaison between the sites and the DCC as needed.

PI's and Study Coordinators from the CCC will perform regular monitoring visits to every site while actively enrolling. Initial monitoring visits will be targeted for after the first 6-8 patients have completed data collection at a given site. A subset of all data points in the online CRFs will be compared with the medical record. Any outstanding data queries will attempt to be resolved with the research coordinator at the time of the visit. After each study site monitoring visit, a report will be prepared and copies sent to the Study File, the DCC, the study PIs, the site PI, the site coordinator and the CCC Study Coordinators.

As part of the overall quality assurance (QA) effort, we will examine various measures of study implementation across sites. In particular, recruitment, retention, data completeness, and measurement precision will be tabulated and compared across sites and will be included in our web-based reports. QA efforts and site visits will be focused on any sites that show evidence of problems.

The DCC will use a web- and email-based reminder system to identify when patients enter a follow-up evaluation window and when evaluations are complete. Data managers from the DCC will assess data quality by running validation checks on a regular basis. Data fields are verified against documented expectations using suitable legal ranges, field requirements, reports, and other data consistency checks. Any discrepancies are reported back to the clinical sites for further review and correction. The reporting page of the study portal will contain a window-based reporting system that checks for the timely entry of data within the anticipated length of neonatal hospitalization (7-20 days) and the schedule of follow-up visits.

